2.3.2 Safety Set

The Safety Set (SS) will include all patients enrolled in the CRAD001M2305 study who have at least one-post CRAD001M2305 baseline safety assessment. It should be noted that all patients enrolled in the CRAD001M2305 study have been exposed to everolimus in the parent study CRAD001M2301 (and may or may not continue receiving commercial everolimus while on CRAD001M2305).

The safety set will be the population used in the assessments of safety, such as adverse events (AEs) and everolimus exposure.

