3.1 General presentation of descriptive summaries

Qualitative data (e.g., gender, race, etc.) will be summarized by appropriate descriptive statistics (i.e. frequencies and percentages); a missing category will be included as applicable. Percentages will be calculated using the number of patients in the relevant population or subgroup as the denominator.

Quantitative data (e.g., age, body weight, etc.) will be summarized by appropriate descriptive statistics (i.e. mean, standard deviation, median, 25th and 75th percentiles, minimum, and maximum).

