3.9.1 Adverse events

AEs which will be counted for a specific period are those which are **treatment-emergent**. These events are those with an onset on or after the start of the treatment period, or which were present prior to the start of the treatment period but increased in severity or developed into SAEs after the start of the treatment period.

AEs collected during the CRAD001M2305 study will be described. All listings and tables will be presented for all CRAD001M2305 patients using the Safety Set.

For CRAD001M2305 patients, using the Safety Set, the overall observation period will be divided into two mutually exclusive segments:

1. everolimus exposure period: from day of first commercial dose received in the CRAD001M2305 study to 30 days after the last commercial dose received in the CRAD001M2305 study.
2. post-everolimus exposure period:
 - starting at day 30+1 after the last commercial dose received in the CRAD001M2305 study
 - or
 - starting at the enrollment date for patients who will stop everolimus in CRAD001M2301 and who will not start commercial everolimus.

The safety summary tables will include only assessments collected during the everolimus exposure period. The safety listings will include all assessments, with those collected during the post-everolimus exposure period being flagged.

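### Adverse event tables limited to the everolimus exposure period use the whole Safety Set as denominator, so on-drug percentages are understated if any patient takes no everolimus in M2305

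*SAP*

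**What the plan says.** **Denominator.** SAP 2.3.2 defines the population: "The Safety Set (SS) will include all patients enrolled in the CRAD001M2305 study who have at least one-post CRAD001M2305 baseline safety assessment". No dose in M2305 is needed, and the definition notes that patients "may or may not continue receiving commercial everolimus while on CRAD001M2305". SAP 3.9.1 assigns this population to the adverse event (AE) output: "All listings and tables will be presented for all CRAD001M2305 patients using the Safety Set". SAP 3.1 gives the general rule: "Percentages will be calculated using the number of patients in the relevant population or subgroup as the denominator".

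**Numerator.** SAP 3.9.1 splits follow-up into two exclusive periods. The first is the "everolimus exposure period: from day of first commercial dose received in the CRAD001M2305 study to 30 days after the last commercial dose". The second is the post-everolimus period, which for some patients covers all of follow-up, "starting at the enrollment date for patients who will stop everolimus in CRAD001M2301 and who will not start commercial everolimus". The section then limits the tables: "The safety summary tables will include only assessments collected during the everolimus exposure period". Events outside the exposure period are listed and flagged only. Protocol 10.5.1.1 and 10.5.1.2 set the same periods and the same limit.

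**A second numerator statement.** SAP 3.9.1.3 opens by allowing only events that began or worsened in the exposure period. Its next sentence also takes in events ongoing at enrollment and during M2305, up to 30 days after the last dose.

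**Patients off drug.** Protocol section 6 requires no treatment. Protocol 2.1 expects some patients to stop everolimus at the end of M2301 and most to continue. Neither document gives a number.

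**The concern.** Under SAP 3.9.1, numerator and denominator describe different groups of patients. A patient who takes no commercial everolimus in M2305 is in the Safety Set and therefore in the denominator. That patient's whole follow-up is post-everolimus, so no event can reach a table restricted to the exposure period, whatever happens to the patient.

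The error can only go one way: it lowers the apparent incidence on drug. It would affect each overall, serious, drug-related and special-interest AE table that follows this rule, including the registry tables in SAP 3.9.1.6, which are also run on the Safety Set. SAP 3.9 rests the secondary safety objective mainly on AE frequency, and the study is a post-authorization safety study requested by the regulator (Protocol 2.1). Neither document provides an exposed-only N for AE tables, an exposure-adjusted rate, or an AE table for the post-everolimus period.

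**Working it through.** **Inputs**

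- N = 15, from SAP 4.2. I assume that all 15 are in the Safety Set.
- k = number of Safety Set patients with no commercial everolimus in M2305. It is not stated. If most patients continue, k is at most 7 of 15; zero is possible. Assumed range: 0 to 7.
- x = number of patients with a given event in the exposure period. Illustration: x = 3.

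**The plan's own figure.** Neither document states an AE rate or an AE denominator. The nearest printed figure is the row for 3 of 15 in the growth-abnormality table of SAP 4.2: 0.20 (0.04, 0.48). The exact binomial (Clopper-Pearson) interval for 3/15 is 4.3% to 48.1%, which agrees. This confirms only N and the interval method; the figure is not in dispute.

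**Formula.** Printed incidence = x/N. Incidence among exposed patients = x/(N−k). The ratio of printed to exposed is (N−k)/N and does not depend on x.

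**Results for x = 3, N = 15**

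| k | Exposed patients (15−k) | Factor (15−k)/15 | Printed 3/15 | Among exposed 3/(15−k) |
|---|---|---|---|---|
| 0 | 15 | 1.00 | 20.0% | 20.0% |
| 1 | 14 | 0.93 | 20.0% | 21.4% |
| 2 | 13 | 0.87 | 20.0% | 23.1% |
| 3 | 12 | 0.80 | 20.0% | 25.0% |
| 5 | 10 | 0.67 | 20.0% | 30.0% |
| 7 | 8 | 0.53 | 20.0% | 37.5% |

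**The 5% listing rule (SAP 3.9.1.6).** At N = 15 a single patient is 1/15 = 6.7%, already above 5%. A smaller denominator only raises this, so the set of listed events does not change.

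**Confidence limits.** If exact limits were printed, the upper limit for 3 patients would move from 48.1% (3/15) to 50.8% at k=1, 57.2% at k=3 and 75.5% at k=7. The AE sections do not call for such limits.

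**SAP 3.9.1 against SAP 3.9.1.3.** Under 3.9.1 and the first sentence of 3.9.1.3, a patient never on commercial drug cannot contribute. Under the second sentence of 3.9.1.3 such a patient might, for example through an event ongoing at enrollment. That sentence ends its window 30 days after the last dose. SAP 2.1.2 takes the last-dose date from the M2305 prescription record, where these patients should have no entry, so for them the window has no defined end.

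**The case against.** **The numerator may be wider.** A reader might infer that patients off drug can never contribute an event. The documents do not support so absolute a statement, because the second sentence of SAP 3.9.1.3 points the other way. The SAP's document history shows that this wording came in with Amendment 1. The treatment-emergent definition in SAP 3.9.1 came in with the same amendment, so the history does not show which should govern. This objection stands: the dilution holds under the SAP 3.9.1 rule, and the conflict must be resolved.

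**k may be zero or one.** Also correct. At k=0 nothing changes, and at k=1 the shift is from 20.0% to 21.4%. The documents do not show that any percentage will in fact be diluted.

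**The confidence limits would be wrong too.** A reader might infer this from the general provisions on 95% intervals in Protocol section 10 and SAP 2.4.2.2. SAP 3.9.1.3 to 3.9.1.5 ask for counts and percentages and name no intervals, so the effect arises only if intervals are printed.

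**SAP 3.1 allows a subgroup denominator.** It does, but SAP 3.9.1 names the Safety Set and all M2305 patients. A programmer would use that N.

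**Readers can rescale.** SAP 3.5 reports how many patients started or are continuing commercial everolimus, and AEs are listed by patient. That softens the problem in a descriptive study of 15 patients with no tests planned on rates. However, the disposition count is on the Full Analysis Set, and the AE tables would still print the diluted percentage.

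**Conclusion.** The mismatch is real as SAP 3.9.1 is written. The tables count only events in the commercial-dose window, while their denominator includes any Safety Set patient who has no such window. Each affected percentage is the exposed-patient incidence times (N−k)/N. With N = 15 and k assumed between 0 and 7, the factor runs from 1.00 down to 0.53. The lower end should not be read as the expected size, since k=7 is the most that a majority continuing would allow.

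The conclusion depends on the SAP 3.9.1 numerator rule being the one applied and on k being above zero. The 5% listing rule is unaffected at N = 15. The correction is still worth making: the bias has one direction, the remedy is cheap, and it changes nothing if k is zero.

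**What to change.** 1. Reconcile SAP 3.9.1 with the two opening sentences of SAP 3.9.1.3, so that a single numerator rule applies to all AE summaries.
2. For every table restricted to the everolimus exposure period, use as denominator the Safety Set patients with at least one commercial everolimus dose in M2305, and print that N in the table.
3. Optionally, tabulate post-everolimus-period events separately with their own N. The table should cover both patients never on commercial drug and patients more than 30 days past their last dose. It needs a footnote: under Protocol 8.2.2, serious events later than 30 days after stopping are reported to the sponsor only when a causal link to everolimus is suspected, so the two periods are not directly comparable.

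The cost of items 1 and 2 is SAP wording, one flag variable and a slightly smaller denominator if k is above zero. Item 3 adds one table. No new data are needed.

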3.9.1.1 Coding of AEs

AEs are coded using the MedDRA terminology.

3.9.1.2 Grading of AEs

AEs will be assessed according to the Common Terminology Criteria for Adverse Events (CTCAE) by using the latest version available at the time of the final analysis. In case of an update of the CTC criteria during the course of the study, some mapping may be necessary.

If CTCAE grading does not exist for an adverse event, the severity of mild, moderate, severe, and life-threatening, corresponding to Grades 1-4, will be used. CTCAE Grade 5 (death) will not be used in this study; rather, information about deaths will be collected through a Death form.

3.9.1.3 General rules for AE Reporting

Summary tables for AEs have to include only AEs that started or worsened during the everolimus exposure period (treatment-emergent AEs). AE summaries will include all AEs ongoing at the time of enrollment and during the Study (CRAD001M2305) and no later than 30 days after the last dose of everolimus. AEs ongoing at the time of enrollment (CRAD001M2305) and during the study will be listed, and AEs starting later than 30 days after the last dose of everolimus will be specifically flagged.

AEs will be summarized by presenting the number and percentage of patients having at least one AE, and having at least one AE in each body system/primary system organ class (SOC_TXT), and for each preferred term (PT_TXT) using MedDRA coding. A patient with multiple occurrences of an AE will be counted only once in the AE category.

Separate AE summaries will be presented by primary system organ class (SOC), PT, and maximum CTC grade (AEVGRD1C). A patient with multiple CTC grades for an AE will be summarized under the maximum CTC grade recorded for the event.

The frequency of CTC grade 3 and 4 AEs will be summarized separately.

Any information collected (e.g., CTC grades, relationship to study drug, action taken) will be listed as appropriate.

3.9.1.4 AE summaries

The following AE summaries will be produced:

- AEs, regardless of study drug relationship, by primary SOC, PT, and maximum grade
- AEs, regardless of study drug relationship, by PT, maximum grade
- AEs, with suspected study drug relationship, by primary SOC, PT, and maximum grade
- Serious adverse events (SAEs), regardless of study drug relationship, by primary SOC and PT, maximum grade
- Adverse events leading to study drug discontinuation, regardless of study drug relationship by primary SOC and PT, maximum grade
- Deaths, by primary SOC and PT

All summaries will show 'All grades' (including AEs with unknown/missing grade) and 'Grades ≥ 3 '.

AEs will be presented in alphabetical order for SOC, and in descending order of frequency for PT within each SOC.

Deaths and AEs will be listed by patient.

3.9.1.5 Adverse events of special interest/ Grouping of AEs

An adverse event of special interest is a grouping of adverse events that are of scientific and medical concern specific to compound Everolimus. These groupings are defined using MedDRA terms, such as SMQs (standardized MedDRA queries), HGLTs (high level group terms), HLT (high level terms) and PTs (preferred terms). Customized SMQs (Novartis MedDRA queries, NMQ) may also be used. A NMQ is a customized group of search terms which defines a medical concept for which there is no MedDRA SMQ available or the available MedDRA SMQ does not completely fit the need. It may include a combination of single terms and/or an existing SMQ, narrow or broad. These searches will be defined in the Novartis tool known as eCRS (electronic Case Retrieval Strategy). The most up-to-date version of the eCRS at the time of analysis is used for retrieval of search terms. A listing of search terms will be provided in the CSR.

For each specified AESI, number (%) of participants with at least one AESI occurring during on-treatment period will be summarized by safety topics, maximum grades.

A listing of all terms down to the MedDRA PTs used to define each AESI will be generated.

3.9.1.6 For the legal requirements of ClinicalTrials.gov and EudraCT

Two required tables on treatment emergent AEs which are not SAEs with an incidence greater than 5%, on treatment emergent SAEs and SAE suspected to be related to study treatment will be provided by SOC and PT on the safety set.

If for a same patient, several consecutive AEs (irrespective of study treatment causality, seriousness and severity) occurred with the same SOC and PT:

- a single occurrence will be counted if there is ≤ 1 day gap between the end date of the preceding AE and the start date of the consecutive AE
- more than one occurrence will be counted if there is > 1 day gap between the end date of the preceding AE and the start date of the consecutive AE

For occurrence, the presence of at least one SAE / SAE suspected to be related to study treatment / non SAE has to be checked in a block e.g., among AEs in a ≤ 1 day gap block, if at least one SAE is occurring, then one occurrence is calculated for that SAE.

Number of deaths resulting from SAEs suspected to be related to study treatment and number of deaths resulting from SAEs irrespective of causality will be provided.

3.9.2 Other safety data

For CRAD001M2305 patients, all data described below will be pooled with the corresponding data from Study CRAD001M2301 **except** for the TAND checklist as this assessment was not collected in the parent study CRAD001M2301.

The other secondary objectives of the study will be based on sexual and neuropsychological (TAND checklist) development data.

The age when patients reach each Tanner Stage II-V will be summarized on the FAS Puberty of Studies CRAD001M2305 and TOSCA.

The following variables will be summarized on the Safety Set (those are only collected in the CRAD001M2305 study) using descriptive statistics:

- age when females will start thelarche
- age when females will have their first menses
- age when males will reach adrenarche

For the age at which Tanner Stage II will be achieved, summary statistics from the KM distribution will be determined on the FAS puberty, including the median age and the proportions of patients reaching this milestone at some given ages. These statistics will be given as point estimates with 95% confidence intervals. The same analyses will be performed for the following variables: age at which each Tanner Stage III, IV and V will be reached. Age at thelarche (females), age at menarche (females) and age at adrenarche (males) will be described similarly on the SS.

Potential delayed puberty will be defined based on Tanner stage and also on onset of menarche for girls. Potential cases identified through this algorithm, will be then clinically reviewed by assessing all available information in order to conclude the clinical relevance of the delay.

Potential delayed puberty in girls is defined as failure to attain Tanner Stage II (for both breast development and pubic hair) by age 13, or absence of menarche by age 15 or within 5 years of attainment of Tanner Stage II [Fenichel 2012] Potential delayed puberty in boys is defined as failure to attain Tanner Stage II (for both testis and pubic hair) by age 14 ([Traggiai 2002], [Tanner 1962])

Rates of potential delayed puberty will be described for boys and girls separately among the patients at risk of delayed puberty along with 95% confidence intervals. The patients at risk are patients who may potentially present an event of potential delayed puberty at baseline.

If the number of patients in CRAD001M2305 is sufficient, the rates of potential delayed puberty will be described in the different subgroups defined by duration of everolimus exposure. These subgroups are described in the Section 3.12.

If a high rate of potential delayed puberty occurs and if the number of patients in the CRAD001M2305 study is sufficient, the duration of exposure and the age at start of everolimus will be summarized using descriptive statistics in the subgroup of patients with potential delayed puberty.

If a high rate of potential delayed puberty occurs and if the number of patients in each study is sufficient, a logistic regression including the duration of exposure and the age at the start of everolimus as continuous covariates will also be used to further explore the relationship between the everolimus exposure and the rate of potential delayed puberty. Additional covariates (e.g. time normalized Cmin) might also be included in the model.

These patients will be clinically reviewed by assessing all available information in order to evaluate their puberty development.

All responses to the individual questions from the TAND Checklist will be summarized using descriptive statistics on both studies, side by side, and over time on the FAS of studies CRAD001M2305 and TOSCA (Research Project 4).

All the responses are categorical in nature from the TAND Checklist, if applicable, the frequency of baseline and worst-post baseline will be summarized on both studies, side by side, and over time on the FAS of studies CRAD001M2305 and TOSCA (Research Project 4).

Safety data from other assessments will be listed, notable values flagged, and any other information collected will be listed as appropriate.

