The dates of all performed brain MRI scans that are done in the scope of the regular TSC SEGA follow-up will be collected at the annual visits. Brain MRI data will not be collected at this point but may be retrieved at a later date if technological advancements pertaining to predicting future cognitive abilities such as the development of the working memory arise.

Brain development will be assessed by determining the occurrence of TSC-Associated-Neuropsychiatric-Disorders (TAND) with an appropriate TAND Checklist at each annual visit.

The first study visit will occur 3 months after enrollment in CRAD001M2305 and the first annual visit one year ( $\pm 30$  days) after enrollment in CRAD001M2305. The 3-monthly visits can be performed per telephone unless a visit to the site is clinically indicated.

Patient participation in the study will be completed once the patient has achieved Tanner Stage V or age 16 for females, age 17 for males, whichever occurs first.

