2.4.2.2 Confidence interval for percentage rates

Endpoints will be summarized in terms of percentage rates with exact 95% confidence intervals. An *exact binomial confidence interval* [Clopper & Pearson, 1934] will be used, implemented using SAS procedure FREQ with the EXACT statement for one-way tables.

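### The delayed-puberty rate keeps in its denominator patients who are never followed to the age at which delay can be seen, so early leaving dilutes it

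*SAP*

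**What the plan says.** SAP 3.9.2 defines the event by age thresholds. For girls it is "failure to attain Tanner Stage II (for both breast development and pubic hair) by age 13, or absence of menarche by age 15", with a further menarche limb that runs five years from Stage II. For boys: "Potential delayed puberty in boys is defined as failure to attain Tanner Stage II (for both testis and pubic hair) by age 14".

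The estimator is a proportion: "Rates of potential delayed puberty will be described for boys and girls separately among the patients at risk of delayed puberty", with a 95% confidence interval. The at-risk group is then defined: "The patients at risk are patients who may potentially present an event of potential delayed puberty at baseline". Protocol 10.5.1.3 says the same. Baseline is the start of everolimus in the parent study (SAP 2.1.4), which may be years before age 13, 14 or 15.

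The general rules do not alter this. SAP 3.1: "Percentages will be calculated using the number of patients in the relevant population or subgroup as the denominator". SAP 2.4.2.2: "Endpoints will be summarized in terms of percentage rates with exact 95% confidence intervals".

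On follow-up, protocol 4.1 states: "Patient participation in the study will be completed once the patient has achieved Tanner Stage V", or age 16 (girls) or 17 (boys) if that comes first. Protocol 7.2.2.2 grants Stage V on either of the two components, so a girl can complete on pubic hair alone. Protocol 7.1.3.1 allows withdrawal at any time.

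SAP 3.9.2 also plans Kaplan-Meier summaries of age at each Tanner stage and at menarche, but does not link them to the delayed-puberty rate.

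**The concern.** Delay is a failure that can be seen only once a child has been observed to the threshold age. The numerator therefore needs follow-up to that age; the denominator does not. Two groups fall in the gap:

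- children who withdraw before 13 or 14, or girls who withdraw before 15;
- girls who complete at Stage V before 15 without menarche. They are assessed on Stage II but remain unclassified on "absence of menarche by age 15 or within 5 years of attainment of Tanner Stage II", unless five years have already passed since Stage II.

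A rate that falls as early leaving rises reassures for the wrong reason. It also serves as a trigger: in SAP 3.9.2 the exposure summary for delayed cases and the logistic regression run only if the rate is high (a level the SAP does not define) and numbers suffice. Recorded exposure also stops at exit, so early leavers would tend to fall in the shorter-exposure subgroups of SAP 3.12, and the dilution need not be even across them.

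**Working it through.** **Plan's own figure.** The SAP states no value for the delayed-puberty rate. The nearest figure by the same method is the N = 15 table in SAP 4.2 (growth abnormality). The exact limits are the 2.5% quantile of Beta(x, n − x + 1) and the 97.5% quantile of Beta(x + 1, n − x).

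| x/n | SAP 4.2 | Recomputed |
|---|---|---|
| 1/15 | 0.07 (0.00, 0.32) | 0.07 (0.002, 0.319) |
| 3/15 | 0.20 (0.04, 0.48) | 0.20 (0.043, 0.481) |

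The method reproduces.

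**Expected crude rate.** Take n patients at risk, true rate p, and a share d leaving before the decision age independently of outcome. Only the n(1 − d) who stay can be seen to be delayed, so cases number np(1 − d) in expectation, and the rate is np(1 − d)/n = p(1 − d). The values of d are assumptions.

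| True p | d = 10% | 20% | 30% | 40% |
|---|---|---|---|---|
| 10% | 9% | 8% | 7% | 6% |
| 20% | 18% | 16% | 14% | 12% |

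**Comparing estimators.** A simulation of Stage II by 13 used about 4,000 patients per scenario. Its assumptions are entry at 6 to 9 years, age at Stage II normal with SD 1.2 years, random leaving at 0.03, 0.06 or 0.10 per year, and follow-up capped at 16. Each row lists results in the order of those three leaving rates.

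| | True risk about 10% | True risk about 20% |
|---|---|---|
| Left before 13 | 15.9 / 27.5 / 42.5% | 15.5 / 27.7 / 42.4% |
| True rate in sample | 9.9 / 9.7 / 9.5% | 20.5 / 19.7 / 19.8% |
| Crude, denominator fixed at baseline | 8.6 / 7.0 / 5.4% | 17.2 / 14.3 / 11.1% |
| Only those followed to 13 | 10.2 / 9.6 / 9.3% | 20.4 / 19.8 / 19.3% |
| Dropping only Stage I leavers | 9.7 / 8.7 / 7.9% | 19.8 / 18.5 / 17.3% |
| 1 − KM attainment at 13 | 10.1 / 9.7 / 9.5% | 20.5 / 19.7 / 19.9% |
| Stage I leavers coded delayed | 19.9 / 26.8 / 37.8% | 30.1 / 37.0 / 46.7% |

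Dropping only Stage I leavers keeps the leavers who had already matured and removes a group enriched for delay, so it stays low. Kaplan-Meier, or requiring follow-up to the decision age, removes the dilution.

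**At the actual size.** Both examples use illustrative counts.

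- 8 girls at risk, 1 case, 2 leaving before 13: 1/8 = 12.5% (0.3 to 52.7) as planned; 1/6 = 16.7% (0.4 to 64.1) among those followed; (1 + 2)/8 = 37.5% if both leavers were delayed.
- 15 at risk, 2 cases, 3 leavers: 2/15 = 13.3% (1.7 to 40.5) against 2/12 = 16.7% (2.1 to 48.4).

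**The case against.** The strongest reply is that the SAP nowhere classes early leavers as not delayed. SAP 3.1 allows a missing category, and SAP 3.8.4 describes patients who reach neither Stage V nor age 16 or 17 as missing. A literal program could even flag every Stage I leaver as having failed to attain, which pushes the rate up. This stands in part: a reader might infer a written rule that counts leavers as not delayed, and there is none. The low rate is the arithmetic result of the stated denominator when leavers are not cases. A missing row does not change that, because SAP 3.1 keeps the whole group as denominator, and SAP 3.8.4 sits under the primary objective.

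A reader might also infer that at-risk status cannot be set where Tanner stage before everolimus is missing. SAP 2.1.5 answers that: the first available assessment after the parent study's amendment 2 serves as baseline.

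Nor is this the main puberty measure. The primary one is Stage V by 16 or 17; delayed puberty is secondary and descriptive, and SAP 2.4.2.1 plans no tests on percentage rates.

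Exposure to the problem is limited too. Planned follow-up runs past the threshold ages, patients who stop everolimus should remain on study (protocol 7.1.3), and SAP 4.2 calls 15 patients too few for any comparison, so the conditional regression is unlikely to run. Finally, SAP 2.4.3.1 gives Kaplan-Meier estimates every 12 months, which would cover 13, 14 and 15 if age is the clock. What is missing is the sex split for Stage II and the link to this rate.

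**Conclusion.** The concern holds as a mismatch between numerator and denominator. As specified, the crude rate is diluted to about p(1 − d) if leaving is unrelated to outcome and leavers are not counted as cases. That is a relative loss equal to d: a true 20% reads 18% at d = 10% and 12% at d = 40%. The actual d and case counts are not in the documents, so the bias in this study cannot be computed. Under the literal reading of failure to attain, the direction reverses, so the claim that the rate must be low in every implementation is not supported.

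With 15 patients split by sex, the shift is small next to the interval width, although one or two unassessable patients visibly move the estimate.

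Two limits apply. Completion at Stage V is itself a pubertal event, so independence is less secure for menarche than for ordinary withdrawal. And this point covers leaving only: patients already at Stage V when the parent study ended could not enrol, which under-represents fast maturers and pulls the other way.

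**What to change.** In SAP 3.9.2:

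1. Make the estimate 1 minus Kaplan-Meier attainment, by sex: Stage II at 13 (girls) and 14 (boys), and menarche at 15, censoring at last assessment, with the intervals of SAP 2.4.3.1. Run it on the patients at risk, with Stage II defined as in the delay criterion, and name the analysis set: SAP Table 2-2 puts delayed puberty on the Safety Set, whereas the Stage II curve is planned on the FAS Puberty.
2. If a crude rate is also shown, restrict its denominator, criterion by criterion, to patients whose follow-up reaches the decision age, whether or not they attained the milestone earlier. Girls who mature and complete at Stage V before that age would also drop out, which can raise this figure; that is a reason to keep it supplementary.
3. Report the number not assessable for each criterion, by sex, and state that leavers are coded neither delayed nor not delayed.
4. Say how the limb of five years from Stage II is handled. It runs on a different clock, so the menarche estimate at 15 does not cover it.

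The cost is SAP wording and a sex split of analyses already planned. No new data are needed. The crude denominator is smaller and its interval somewhat wider, and the criterion-specific estimates do not sum to one combined rate for girls.
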